**Standard mood ratings sent once per week:** - 1) *"Hi Miguel, this is [name]. How is your mood today? Reply with a number from 1 (poor) to 5 (Excellent) when convenient."* "Thank you for the response. Remember, doing a social activity like talking to a friend can help you feel better."

**Problem-Solving Messages:** *"Hi Miguel, do you need any help remembering the activities you planned? Reply Y for Yes, N for No."* "You replied Y. You mentioned wanting to call to chat with your brother." "Can you do that today?" "How is your homework going? Can I help you in any way with the homework?" "Remember, rate how you are feeling. Let me know if you need help with the ratings." "If you have an emergency, please call 911."

**Data Collection** - All study phones will store text-message communication and will be downloaded from the smart phone into a Microsoft Word document. From this document, all responses are then pasted into a secure and password protected Microsoft Excel file. The excel file lists all participant unique ID numbers, message history, and schedule preferences. The file is stored on the UCSF Box cloud storage.

---

#### 6.1.2 ADMINISTRATION AND/OR DOSING

We are taking a brief behavioral intervention for depression, a text-message support intervention, and a cognitive-behavioral intervention, and sequencing how each is rolled out based on how participants respond. In a traditional approach, we would be comparing each component individually as standalone interventions compared to a control condition, and evaluating their effects. In a SMART, you start with the lowest burden/low dose intervention, and only increase as needed. This study is solely focused on feasibility and acceptability.

There are situations where multiple treatments are known to be effective, but what is unknown is whether every person benefits the same from all of them. In the depression field, we do not know how best to package what are considered efficacious interventions - 1) behavioral activation therapy, 2) cognitive-behavioral therapy, and 3) text-message support to treat depression and promote adherence to medication and clinic appointments. We will use a SMART design to evaluate if it is feasible and acceptable to sequence these behavioral interventions for depression.

**STARTING POINT:** Patients are recruited and then randomized to one of two active arms. The first randomization is to one of two interventions (A1 and A2). Both A1 and A2 are an already-established efficacious brief behavioral intervention, the only difference is that one will include a text-message support intervention (A1 versus A2 + Text-message support), which is the experimental factor we are testing, i.e., whether text-message support is the key factor between A1 and A2. At baseline, where participants are randomized, we will measure their depression using a standard rating scale.

**FIRST OPTION:** All participants will complete 4 of 8 sessions of A1 or A2, at which point we will make another depression assessment. This assessment will indicate if participants responded well to this first "assignment" (i.e., improved depression ratings) or did not respond well (i.e., no change in depression ratings or worse depression ratings). If they respond well, nothing changes and they proceed as normal through the 5-session program. If they do not respond, i.e., show no improvement or show worse ratings, we "adapt" the intervention because we have evidence that the intervention is not currently relieving depressive symptoms.

**SECOND OPTION:** If participants do not respond to their first assignment (e.g., no change in depression ratings or worse ratings), they are eligible to be randomized again to a second assignment (B1, B2, B3, or B4). This is why the term "sequential multiple assignment" is used because the goal is to identify how to start with A1 and "sequence" other intervention components through an "assignment" to "multiple" components (B1-B4).

**Participants who did not respond to A1 or A2 (only difference is A2 has text-message support) have four options:**

1. If participants in the A1 arm DO NOT improve, they can be re-randomized to either B1 to receive the text-message support component; or
2. B2 to switch to more intensive intervention, which is known as cognitive-behavioral therapy and text-message support.
3. If participants in the A2 arm DO NOT improve, they can be re-randomized to either B3 to receive one booster session of same program; or
4. B4 and switch to more intensive intervention of cognitive-behavioral therapy & text-message support.

The components are: 1) a brief Behavioral Activation Therapy (BAT), 2) cognitive-behavioral therapy (CBT), and a text-messaging tool (mHealth).

Patients (N=45) will first be randomly assigned to the first intervention component of either: A1) BAT by itself or A2) BAT & text-message support.

**DICTATING CHANGE:** At the first follow-up point, which is half-way through the first assignment, we will make an assessment of how they responded to the first intervention. Our goal is to measure changes in their depression ratings using a cut-off score on a clinical depression assessment tool. If their depression ratings have improved, they will maintain their initial treatment (Stay with A1 or A2), which is either: 1) BAT by itself or 2) BAT & text-message support.

If their depression ratings have not improved or get worse, we will re-randomize them to one of four additional components they have not received: B1-B4.

**To summarize:** BAT and CBT and mHealth are efficacious approaches to helping patients self-manage their depression. However, rather than given all patients a complex package (CBT with mHealth), we are seeking to evaluate the feasibility and acceptability of starting with a brief intervention, and then sequentially to add more intensive components only when needed.

## 6.2 FIDELITY

### 6.2.1 INTERVENTIONIST TRAINING AND TRACKING

We have two licensed psychologists and a trained cognitive-behavioral therapist on the research team who are supervising all activities. We are also using a published fidelity monitoring coding sheet to score adherence to the intervention. Interventionist will write Data-Assessment-Plan notes (DAP) for each session, which is discussed in weekly team meetings and additional trainings are discussed if fidelity to the intervention is sub-optimal.

## 6.3 MEASURES TO MINIMIZE BIAS: RANDOMIZATION AND BLINDING

All randomization is done blinded. Prior to the start of the intervention, we will use the National Cancer Institutes Clinical Trial Randomization Tool stratified by English and Spanish. These randomizations will be relayed to the study coordinator who will inform the participant of their intervention starting point.

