### 1.2 SCHEMA

***Flow Diagram - See Attached Figure of Sequential Multiple Assignment Randomized Trial Design.***

## 1.3 SCHEDULE OF ACTIVITIES

	Pre-screening (Pre-consent)	Visit 1 Day 1	Visit 2 Day 7	Visit 3 Day 14 ±7	Visit 4 Day 21 ±7	Visit 5 Day 28 ±7	Visit 6 Day 35 ±7	Visit 7 Day 42 ±7	Visit 8 Day 49 ±7	Visit 9 Day 56 ±7	Visit 10 Day 63 ±7	Visit 11 Day 70 ±7	Final Visit Day 84 ±7
Screen for Eligibility	X												
Informed Consent		X											
Demographics		X											
Depression and Text-Message Criteria		X					X						
Outcome Evaluation													
Depression Ratings		X	X	X	X	X	X	X	X	X	X	X	X
Randomization		X		X									
1 st Stage Intervention		X	X	X	**	X*	X* 						
Primary Tailoring Variable - Decision Point on Sequencing				X									
2 nd Stage Intervention					X	X	X*	X*	X*	X*	X*	X*	
Adverse Events Reporting			X	X	X	X	X	X	X	X	X	X	X

\*Participants will all start with the first stage treatment - This is BAT with or without text-messaging support. After 3 of 5 sessions - approximately half-way through the intervention - their depression ratings are assessed that specifically inform the next course - This is called the second-stage treatment. Participants may either continue to complete the 5 sessions their first-stage treatment (i.e., BAT), get one extra booster session (denoted by \*1), or switch to CBT, which includes up to 11 sessions (denoted by \*).

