Conversely, participants randomized to the (A2) BAT & text-message support will receive an identical BAT program with the addition of one and two-way personalized text messages that will be delivered twice a week to facilitate engagement with the intervention activities.

**Text-Messages** - One-way messages will be sent as appointment and BAT adherence reminders (e.g., "Please remember to fill out your social activity planner?", while two-way text messages will be sent as "check-ins" with participants in the form of a mobile interventionist (e.g., "How is your activity planning going? If you need assistance, I can remind you of what activities you said you could do"). Participants will be asked to respond to these two way-text messages at their earliest convenience.

After three sessions of the five planned sessions have been completed, an assessment of the participants depression will be made using a cutoff score on the Patient Health Questionnaire-9 (PHQ-9), a self-reported rating scale for depression (this is called a "primary tailoring variable"). This primary tailoring variable will dictate the second sequence. Based on their PHQ-9 score, participants are coded as a "responder" or "non-responder;" a code that dictates whether their initial randomization assignment is 1) maintained, 2) augmented, or 3) switched to a second component (this is the second randomization and "adaptive" component).

**Participants who were randomized to BAT alone and were coded as "non-responders" will be randomized to:** 1. additionally receive text-message support, or 2. switched to receive CBT & text-message support. If switched to CBT & text-message support, participants will complete a total of eight intervention sessions that can be re-arranged to fit patient needs. CBT sessions will be scheduled once a week for 60 minutes (as described above, CBT integrates cognitive theory principles with behavioral theory principles, and thus, is more intensive). If participants randomized to BAT alone during their first stage of treatment and responded, they continue with maintenance of their BAT sessions.

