### 9.2 SAMPLE SIZE DETERMINATION

Daniel Almirall is a leading expert in SMART designs and developed a sample size estimation tool specifically for pilot SMARTs. First, we propose six treatment sequences and a minimum of four participants to receive them (called “outcome groups” in Figure 1). Second, one must estimate from the literature the percentage of participants who will not show a clinically meaningful response (i.e., “non-response rate”) to a treatment they will be initially randomized to. We used data from a non-inferiority trial of cognitive therapy versus a behavioral activation therapy in general population sample. This trial used clinician-administered diagnostic tools, self-report ratings, fidelity monitoring, and had all interventions delivered by psychologists and social workers. Under these rigorous conditions, 50-60% of participants with mild depression at baseline (range based on self-report and clinician ratings) did not achieve a 50% reduction in depressive symptoms at a 4-month follow-up. Similar results were found for participants with a higher severity of depression at baseline. This estimation tool yielded a total sample size of 45 participants if we observe a non-response rate of 50-60%, a fixed probability of 80% (suggested by Almirall), a minimum of four participants per “outcome group,” and a 10% attrition rate.

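### Does N=45 rest on a second-stage randomisation scheme that sections 6.3 and 9.2 never describe?

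*Combined protocol and SAP*

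**What the plan says.** Section 9.2 sets the design target: "we propose six treatment sequences and a minimum of four participants to receive them". The sizing tool "yielded a total sample size of 45 participants if we observe a non-response rate of 50-60%, a fixed probability of 80" per cent, with four per outcome group and 10% attrition. The non-response range comes from a trial in which 50-60% of participants with mild depression "did not achieve a 50% reduction in depressive symptoms at a 4-month follow-up".

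Section 6.3 gives the randomisation method: "Prior to the start of the intervention, we will use the National Cancer Institutes Clinical Trial Randomization Tool stratified by English and Spanish". It continues: "These randomizations will be relayed to the study coordinator who will inform the participant of their intervention starting point".

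The second randomisation is planned. The schedule in section 1.3 marks it in the Day 14 column, in line with the row "Primary Tailoring Variable - Decision Point on Sequencing". Section 6.1.1 links it to the PHQ-9 responder code ("this is the second randomization and" the adaptive component, in its terms) and gives each first-stage arm two options for non-responders. Section 6.1.2 lists the same options, B1 or B2 after A1 and B3 or B4 after A2, and then says "we will re-randomize them to one of four additional components they have not received: B1-B4".

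Section 9.1 states that there are no hypotheses. Section 9.4.1 and the SAP analyse feasibility descriptively, including 80% retention in all outcome groups.

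**The concern.** In a SMART the second randomisation fills the smallest groups. Here the visible text gives no ratio, blocking or list for it; the design figure cannot be seen. Filling the six sequences is also the only quantitative basis for 45. If the 80% is a joint probability, the allocation scheme matters a great deal: with 40 completers, an even split gives 75 to 93% over the stated non-response range, and simple allocation gives 33 to 60%. The timing of attrition matters too. The schedule puts the decision at Day 14 of 84, so much of the 10% loss could come after the second randomisation and thin groups already formed. A reader could conclude that 45 depends on an even split that nobody has committed to, and that the stated probability is too high.

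**Working it through.** **Inputs.** From section 9.2: N=45, six groups (two responder, four non-responder), at least four per group, probability 80%, non-response q of 50-60%, attrition 10%. Assumed, because the text is silent: 1:1 allocation at both stages, independent responses, and loss unrelated to response. Completers: 45 × 0.9 = 40.5, so 20+20 or 20+21 per arm.

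**Reading 1: the 80% is joint and the second split is even.** With X non-responders among n in an arm, X ~ Bin(n, q). Both second-stage groups reach four if X ≥ 8, and the responder group reaches four if X ≤ n − 4. The joint value is the product of P(8 ≤ X ≤ n − 4) over the two arms.

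For n=20 and q=0.50: P(8 ≤ X ≤ 16) = 1 − 0.1316 − 0.0013 = 0.867, and 0.867² = 0.752.

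The smallest number of completers giving a joint 80% is 42, 38 and 36 at 50, 55 and 60%. Dividing by 0.9 gives 46.7, 42.2 and 40, so **47, 43 and 40** enrolled. With 50% in one arm and 60% in the other, 40 completers are needed, and 40/0.9 = 44.4 gives exactly 45.

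**Reading 2: the 80% applies to each group and allocation is simple 1:1.** A second-stage group has size Bin(n, q/2), and P(size ≥ 4) must be at least 0.80. The responder groups do not bind: with n=20 and q=0.60, P(at least four responders) = 0.984.

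| Non-response | n per arm | P(size ≥ 4) | Completers | Divided by 0.9 | Enrolled |
|---|---|---|---|---|---|
| 50% | 21 | 0.808 | 42 | 46.7 | **47** |
| 55% | 19 | 0.810 | 38 | 42.2 | **43** |
| 60% | 18 | 0.835 | 36 | 40.0 | **40** |

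The two readings give identical enrolment, and 45 lies inside the range of both. The fit to 45 therefore cannot show which reading was used, and it does not imply an even split. Only a joint reading with simple allocation is clearly out of line, at 64, 57 and 53 enrolled.

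**Joint probability at 45 enrolled, 10% loss unless stated.**

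| Assumption | 50% | 55% | 60% |
|---|---|---|---|
| Even split, loss before it, 20+20 | 75% | 88% | 93% |
| Even split, loss before it, 20+21 | 78% | 90% | 94% |
| Even split, late drop-outs counted as having received the sequence, 22+23 | 89% | 96% | 98% |
| Blocks of four within arm, all loss afterwards and not counted | 65% | 79% | 86% |
| Simple allocation, loss before it, 20+20 | 33% | 47% | 60% |

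In the first two rows the value reaches 80% at about 52% and 51% non-response.

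**Timing.** Day 14 is only one of the decision times given. Section 8.1 refers to four weeks, or four of eight sessions, and also to three of five sessions. Section 6.1.2 says four of eight. Section 6.1.1 says three sessions, held every two weeks, which is about four weeks if the first is at the start. A later decision leaves less loss to fall after it. Section 9.2 speaks of participants who receive a sequence, so whether a late drop-out counts is open; the third and fourth rows show the two answers.

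**The one-of-four sentence.** Taken literally, it would send A2 participants to B1, the text messages they already have, although the sentence limits the choice to components not yet received. The arm-specific list just above it and the matching text in section 6.1.1 settle the meaning. It is loose wording.

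**The case for a change.** The strongest case for a change is that staff could use simple allocation at the second stage without departing from the protocol, and a joint probability would then be 33 to 60%. Section 7.2 lets randomised participants who never start be replaced, so the losses that count tend to be later ones, which points towards the 65/79/86% row. The general statement in section 6.3 that randomisation is blinded describes no concealment at the decision point. A few sentences would settle all of this.

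What stands is that the 80%, the timing of attrition and the second-stage method are undefined in the visible text. The inference that 45 needs an even split does not stand, since the per-group reading gives the same numbers without one. The low figures combine the joint reading with a scheme that the documents do not state, and the late-loss figures hold only if late drop-outs are not counted.

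The link to the retention outcome is also weak. That outcome is a proportion within each group, not a minimum count. One loss in a group of three leaves 2/3 = 67%, and one in a group of four leaves 3/4 = 75%; both are below 80%. Reaching four does not protect the criterion.

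**Conclusion.** The concern does not call for a change. The plan leaves out detail, but 45 agrees roughly with two natural readings of section 9.2, and exactly with one of them if the arms have 50% and 60% non-response. On the joint reading with an even split and early loss, the shortfall is 2 to 5 percentage points at exactly 50% non-response and disappears by about 52%. These values assume 1:1 allocation, independent responses and loss unrelated to response.

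Little hangs on the exact probability. No hypothesis is tested, the outcomes are counts and proportions, and a sequence with three participants would be reported as such, which is itself a feasibility finding. A team that already uses a randomisation tool can be expected to draw the second assignment between the two options of the participant's own arm. Writing particular probabilities into section 9.2 would mean choosing among readings that the documents leave open. The conflicting decision times are a separate matter, and those sections must be reconciled on their own account.

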## 6.4 STUDY INTERVENTION/EXPERIMENTAL MANIPULATION ADHERENCE

The acceptability outcomes are what is being evaluated to determine adherence to the intervention. Acceptability: 1) > 90% adherence to the BAT and CBT session schedule; 2) responsiveness to text messages as: a) >80% of all two-way messages replied to during the set of blocked hours; b) >90% of participants reporting direct benefit from one-way text-messages; 3) positive responses coded from post-intervention exit interview transcripts; 4) limited number of barriers to participation reported in exit interviews; and 5) responses to a brief survey (to be developed) assessing clinic staff acceptability of the intervention. Given the focus on feasibility and acceptability, the focus remains on studying whether these adherence markers can be achieved.

## 6.5 CONCOMITANT THERAPY

All participants will be able to receive pharmacotherapy, other psychotherapy, case management and social work services during the study, as this does not affect their eligibility and reflects the real-world circumstances of patients who may benefit from our study in the future. The implementation of the pilot SMART at ZSFG will integrate an adaptive intervention into an HIV care site, and use Spanish and English text-messages to promote adherence to the intervention. Importantly, this study will not interfere in any way with the standard of HIV primary care regularly received by patients at the ZSFG Ward 86 Clinic. Participants in a SMART are randomized to an evidence-based treatment intervention for depression, with the only differentiating factor being the use of text-messaging to support

adherence to the intervention's protocol. It is only when a patient does not respond to their assigned treatment do we investigate the next course of action in the form of a second-stage treatment, which is adapted to their particular case. Furthermore, no other services for depression, including pharmacotherapy, will be denied. For each patient, we are writing a formal letter to their HIV care provider to let them know that their patient is in this study because they reported mild to moderate depression severity and to continue to prescribe any treatment they deem appropriate. **All together, we believe that our study design, and feature of not withholding any treatment, does not place any participant at greater risk than what they would encounter with any other services available for their depression.**

#### 6.5.1 RESCUE THERAPY

*Not applicable*

### 7 STUDY INTERVENTION/EXPERIMENTAL MANIPULATION DISCONTINUATION AND PARTICIPANT DISCONTINUATION/WITHDRAWAL

#### 7.1 DISCONTINUATION OF STUDY INTERVENTION/EXPERIMENTAL MANIPULATION

All participants who wish to discontinue the study will be asked for the reasons for discontinuing. This is part of the evaluation. If a clinically significant finding is identified (including, but not limited to changes from baseline) after enrollment, the investigator or qualified designee will determine if any change in participant management is needed. This is part of the Data and Safety Plan that was submitted to the NIH and approved (This file is available upon request). Any new clinically relevant finding will be reported as an adverse event (AE).

The data to be collected at the time of study intervention discontinuation will include the following:

- The reason(s) for discontinuing the participant from the intervention, and methods for determining the need to discontinue.
- If the participant is due to complete the first assessments within 2 weeks of being discontinued from the study intervention (asking to stop with the intervention activities but willing to come in for the assessment), those assessments will be administered at the time of discontinuation; if the next scheduled assessments are more than 2 weeks from the discontinuation date, the discontinued participant will wait for the next scheduled assessment (unless they wish to completely discontinue with all study activities). Thereafter, the participant will be included in all future scheduled assessments, even though not participating in the intervention.

#### 7.2 PARTICIPANT DISCONTINUATION/WITHDRAWAL FROM THE STUDY

Participants are free to withdraw from participation in the study at any time upon request.

An investigator may discontinue a participant from the study for the following reasons:

- Significant study intervention non-compliance, unless varying compliance is an aspect of the study objectives

- Lost-to-follow up; unable to contact subject.
- Any event or medical condition or situation occurs such that continued collection of follow-up study data would not be in the best interest of the participant or might require an additional treatment that would confound the interpretation of the study.
- The participant meets an exclusion criterion (either newly developed or not previously recognized) that precludes further study participation.

The reason for participant discontinuation or withdrawal from the study will be recorded. Subjects who sign the informed consent form and are randomized but do not receive the study intervention may be replaced. Subjects who sign the informed consent form, and are randomized and receive the study intervention, and subsequently withdraw, or are discontinued from the study.

